#### **8.4.8 *Initial Follow-Up Period: Week 6***

- ECOG performance status
- Vital signs
- Physical examination
- Adverse events
- Weight
- Concomitant medications
- Hematology panel
- Serum chemistry panel
- Research bloods
- Tumor markers
- Tumor Biopsy
- Imaging studies for tumor response. If radiographic PD is detected at 6 weeks, PD must be confirmed with repeat imaging 4 weeks later. In case of slow tumor growth, the investigator may wait until confirmation of the PD at 12 weeks to resume chemotherapy. In case of unequivocal progression, the investigator may resume chemotherapy prior to 12 weeks and the subject will be considered as treatment failure at 12 weeks.

#### **8.4.9 *Initial Follow-Up Period: Week 12***

- ECOG performance status
- Vital signs
- Physical examination
- Adverse events
- Weight
- Concomitant medications (including any new anti-cancer therapies)

- Hematology panel
- Serum chemistry panel
- Research bloods
- Tumor markers
- Imaging studies for tumor response

#### ***8.4.10 Long-Term Follow-Up Period: Week 18***

- Imaging studies for tumor response

#### ***8.4.11 Long-Term Follow-Up Period: Week 24***

- Imaging studies for tumor response

#### ***8.4.12 Long-Term Follow-Up Period: Week 36***

- Imaging studies for tumor response

#### ***8.4.13 Long-Term Follow-Up Period: Week 48***

- Imaging studies for tumor response

## **9 TUMOR RESPONSE ASSESSMENTS**

Tumor response is based on the RECIST v.1.1. A copy of the full article is provided as [Appendix 16.3](#). Key elements of the criteria are summarized below. Tumor response will also be assessed by Immune-Related Response Criteria (irRC) ([Wolchok et al, 2009](#)).

### **9.1 Measurability of Tumor at Baseline**

RECIST v.1.1 provides the following definitions for designating the tumor lesion/lymph node as measurable or non-measurable at baseline.

#### ***9.1.1 Measurable Lesions***

##### **9.1.1.1 Tumor Lesions**

Must be accurately measured in at least one dimension (longest diameter in the plane of measurement is to be recorded) with a minimum size as follows:

- 10 mm by CT scan (CT scan slice thickness no greater than 5 mm; see Appendix II of [Eisenhauer et al, 2009](#) for imaging guidance)
- 10 mm caliper measurement by clinical exam (lesions which cannot be accurately measured with caliper should be recorded as non-measurable)
- 20 mm by chest X-ray

#### 9.1.1.2 Malignant Lymph Nodes

To be considered pathologically enlarged and measurable, a lymph node must be  $\geq 15$  mm in short axis when assessed by CT scan (CT scan slice thickness recommended to be no greater than 5 mm). At baseline and in follow-up, only the short axis will be measured and followed. For additional information on lymph node measurement, see notes in [Eisenhauer et al, 2009](#) under the heading “Baseline documentation of target and non-target lesions,” as well as a companion paper on lymph node assessment using RECIST ([Schwartz et al, 2009](#)).

#### 9.1.2 *Non-measurable Lesions*

Non-measurable lesions are all other lesions, including small lesions (longest diameter  $< 10$  mm or pathological lymph nodes with  $\geq 10$  to  $< 15$  mm short axis) as well as truly non-measurable lesions. Truly non-measurable lesions include leptomeningeal disease, ascites, pleural or pericardial effusions, inflammatory breast disease, lymphangitic involvement of skin or lung, and abdominal masses/abdominal organomegaly identified by physical exam that is not measureable by reproducible imaging techniques.

#### 9.1.3 *Special Considerations Regarding Lesion Measurability*

Bone lesions, cystic lesions, and lesions previously treated with local therapy require particular comment.

##### 9.1.3.1 Bone Lesions

Bone scan, PET scan, or plain films are not considered adequate imaging techniques to measure bone lesions. However, these techniques can be used to confirm the presence or disappearance of bone lesions.

Lytic bone lesions or mixed lytic-blastic lesions, *with identifiable soft tissue components*, that can be evaluated by cross-sectional imaging techniques such as CT or MRI can be considered as measurable lesions if the soft tissue component meets the definition of measurability described above.

Blastic bone lesions are non-measurable.

##### 9.1.3.2 Cystic Lesions

Lesions that meet the criteria for radiographically defined simple cysts should not be considered as malignant lesions (i.e., neither measurable nor non-measurable) since they are, by definition, simple cysts.

Cystic lesions thought to represent cystic metastases can be considered as measurable lesions if they meet the definition of measurability described above. However, if non-cystic lesions are present in the same individual, these are preferred for selection as target lesions.

### 9.1.3.3 Lesions with Prior Local Treatment

Tumor lesions situated in a previously irradiated area, or in an area subjected to other loco-regional therapy, are usually not considered measurable unless there has been demonstrated progression in the lesion.

### 9.1.4 *Methods of Tumor Measurement*

Please refer to [Eisenhauer et al, 2009, Section 3.2](#) for details concerning details of how measurements of lesions/lymph nodes should be done. For the current study, CT is the only acceptable measurement method.

## 9.2 Tumor Response Evaluation

### 9.2.1 *Designation of Target and Non-Target Lesions*

When more than one measurable lesion is present at baseline, all lesions, up to a maximum of 5 lesions (and a maximum of 2 lesions per involved organ) representative of all involved organs should be identified as target lesions and will be recorded and measured at baseline. In the current study, the baseline measurement will be based on the scans and measurements taken at the end of the pre-study standard chemotherapy, as submitted by the investigator.

**Study entry requires the presence of at least 2 measurable lesions at baseline, one of which will be injected with Ad-RTS-hIL-12 and the other of which will be followed for response. Per RECIST v.1.1 (see [Appendix 16.3](#)), the injected lesion must be considered a non-target lesion. Remaining measurable lesions should be designated as target or non-target lesions as described above.**

Target lesions should be selected on the basis of their size (lesions with longest diameter) and be representative of all involved organs, but in addition should be those that lend themselves to reproducible repeated measurements. It may be the case that on occasion, the largest lesion does not lend itself to reproducible measurement; in such cases, the next largest lesion that can be reproducibly measured should be selected.

A sum of the diameters (longest for non-nodal lesions, short axis for nodal lesions) for all target lesions will be calculated and reported as the baseline sum diameters. The baseline sum diameters will be used as the reference to characterize any objective changes in the measurable dimension of disease.

All other lesions or sites of disease (i.e., non-measurable lesions), including pathological lymph nodes, should be identified as non-target lesions. Measurements of non-target lesions, even if measurable, are not required, as they are intended to be assessed qualitatively and should be designated as present or absent at baseline. It is also possible to record multiple non-target lesions in the same organ as a single item, e.g., “multiple enlarged pelvic lymph nodes.”

## 9.2.2 Definitions of Response

### 9.2.2.1 Target Lesions

Definitions of response for individual patients at each assessment time point for target lesions are shown in [Table 9.2.2.1-1](#).

**Table 9.2.2.1-1 Evaluation of Response in Target Lesions**

Response Category	Definition
CR	Disappearance of all target lesions. Any pathological lymph nodes (whether target or non-target) must have reduction in short axis to < 10 mm.
PR	At least a 30% decrease in the sum of diameters of target lesions, taking as reference the baseline sum diameters.
PD	At least a 20% increase in the sum of diameters of target lesions, taking as reference the smallest sum on study (this includes the baseline sum if that is the smallest on study). In addition to the relative increase of 20%, the sum must also demonstrate an absolute increase of at least 5 mm. (Note: the appearance of one or more new lesions is also considered progression). For this study, PD should be confirmed at least 4 weeks later.
SD	Neither sufficient shrinkage to qualify for PR nor sufficient increase to qualify for PD, taking as reference the smallest sum diameters while on study

Abbreviations: CR, complete response; PR, partial response; PD, progressive disease; SD, stable disease

### 9.2.2.1.1 Lymph Nodes as Target Lesions

Please refer to RECIST v.1.1 in [Appendix 16.3](#) for special notes on the assessment of lymph nodes as target lesions, lesions that become too small to measure, and lesions that split or coalesce after treatment.

### 9.2.2.2 Non-target Lesions

Definitions of response for individual patients at each assessment time point for non-target lesions are shown in [Table 9.2.2.2-1](#). Non-target lesions, even if measurable, are to be evaluated qualitatively, as noted above, and are to be designated as CR, non-CR/non-PD, or PD, as defined in [Table 9.2.2.2-1](#).

**Table 9.2.2.2-1 Evaluation of Response at Each Time Point in Non-target Lesions**

Response Category	Definition
CR	Disappearance of all non-target lesions and normalization of tumor marker level. All lymph nodes must be non-pathological in size (<10 mm short axis).
Non-CR/Non-PD	Persistence of one or more non-target lesion(s) and/or maintenance of tumor marker level above the normal limits.
PD	Unequivocal progression (see comments below) of existing non-target lesions. (Note: the appearance of one or more new lesions is also considered progression). a

Abbreviations: CR, complete response; SD, stable disease; PD, progressive disease.

a Although a clear progression of “non-target” lesions only is exceptional, in such circumstances, the opinion of the treating physician should prevail.

#### **9.2.2.2.1      *Special Notes on Designation of Progression in Non-Target Disease***

The concept of progression of non-target disease in the setting of concurrent measurable disease as in this study requires further explanation. In this setting, to assign unequivocal progression on the basis of the non-target disease (see determination of overall response in [Section 9.2.2.5](#)), there must be an overall level of substantial worsening in non-target disease such that, even in the presence of SD or PR in the target disease, the overall tumor burden has increased sufficiently to warrant discontinuation of therapy (see examples in the RECIST v.1.1 guidelines in [Appendix 16.3](#)). A modest increase in the size of one or more non-target lesions is usually not sufficient to qualify for a designation as unequivocal progression. The designation of overall progression solely on the basis of change in non-target disease in the face of SD or PR of target disease will therefore be extremely rare.

#### **9.2.2.3      New Lesions**

The appearance of new malignant lesions denotes disease progression. Refer to RECIST v.1.1 in [Appendix 16.3](#) for notes concerning the detection of new lesions.

#### **9.2.2.4      Missing Data**

When no imaging/measurement is done at all at a particular time point, the subject is not evaluable (NE) at that time point. If only a subset of lesion measurements is made at an assessment, usually the case is also considered NE at that time point, unless a convincing argument can be made that the contribution of the individual missing lesions would not change the assigned time point response. This would be most likely to happen in the case of PD. For example, if a subject had a baseline sum of 50 mm with three measured lesions and at the assessment only two lesions were assessed, but those gave a sum of 80 mm, the subject will have achieved PD status regardless of the contribution of the missing lesion measurement.

#### **9.2.2.4.1      *Additional Notes Relevant to Designations of Disease Progression***

Per RECIST v.1.1, patients with a global deterioration of health status requiring discontinuation of treatment without objective evidence of disease progression should be reported as “symptomatic deterioration,” and every effort should be made to document objective progression

even after discontinuation of treatment. Symptomatic deterioration is not a descriptor of an objective response; it is a reason for stopping study therapy. The objective response of such subjects is to be determined by evaluation of target and non-target disease as shown in [Table 9.2.2.1-1](#) and [Table 9.2.2.2-1](#). In the current study, scans are to be done at week 6 and 12 weeks, and at any time deemed appropriate by the investigator (i.e., when progression is suspected). PD at week 6 must be confirmed at least 4 weeks later. The definition of progression rate for this study, is given in [Section 12.4.3.2](#).

#### 9.2.2.5 Overall Response for Each Subject at Each Assessment Time Point

Overall response at each assessment time point is based on the totality of the responses for target and non-target lesions, as shown in [Table 9.2.2.5-1](#).

**Table 9.2.2.5-1 Rubric for Determination of Overall Response at Each Assessment Time Point for Each Patient**

Target Lesions	Non-target Lesions	New Lesions	Overall Response
CR	CR	No	CR
CR	Non-CR/non-PD	No	PR
CR	Not evaluated	No	PR
PR	Non-PD or not all evaluated	No	PR
SD	Non-PD or not all evaluated	No	SD
Not all evaluated	Non-PD	No	NE
PD	Any	Yes or No	PD
Any	PD	Yes or No	PD
Any	Any	Yes	PD

Abbreviations: CR, complete response; PR, partial response; SD, stable disease; PD, progressive disease

#### 9.2.2.6 Additional Information Concerning RECIST v1.1

Full details concerning the use of RECIST v.1.1 may be found in the full article by [Eisenhauer et, al \(2009\)](#), which is attached as [Appendix 16.3](#).

#### 9.2.2.7 Immune Related Response Criteria (irRC)

At the baseline tumor assessment, the sum of the products of the two largest perpendicular diameters (SPD) of all index lesions (five lesions per organ, up to 10 visceral lesions and five cutaneous index lesions) is calculated. At each subsequent tumor assessment, the SPD of the index lesions and of new, measurable lesions ( $\geq 5 \times 5$  mm; up to 5 new lesions per organ: 5 new cutaneous lesions and 10 visceral lesions) are added together to provide the total tumor burden:

Tumor Burden = SPDindex lesions + SPDnew, measurable lesions

Percentage changes in tumor burden per assessment time point describe the size and growth kinetics of both conventional and new, measurable lesions as they appear. At each tumor assessment, the response in index and new, measurable lesions is defined based on the change in tumor burden (after ruling out irPD). Decreases in tumor burden must be assessed relative to baseline measurements (i.e., the SPD of all index lesions at screening).

Overall response using the irRC: The overall response according to the irRC is derived from time-point response assessments (based on tumor burden) as follows:

- irCR, complete disappearance of all lesions (whether measurable or not, and no new lesions) confirmation by a repeat, consecutive assessment no less than 4 weeks from the date first documented
- irPR, decrease in tumor burden  $\geq 50\%$  relative to baseline confirmed by a consecutive assessment at least 4 weeks after first documentation
- irSD, not meeting criteria for irCR or irPR, in absence of irPD
- irPD, increase in tumor burden  $\geq 25\%$  relative to nadir (minimum recorded tumor burden) confirmation by a repeat, consecutive assessment no less than 4 weeks from the date first documented

## 10 SAFETY ASSESSMENTS

### 10.1 Adverse Events (AEs) and Definitions

*Adverse Event:* Any untoward medical occurrence in a patient or clinical investigation subject administered a pharmaceutical product that does not necessarily have a causal relationship to the treatment. An AE can therefore be any unfavorable and unintended sign including an abnormal laboratory finding, symptom, or disease temporarily associated with the use of a medicinal product, and any worsening of pre-existing conditions, regardless of causality to the medicinal product.

*Suspected Adverse Reaction:* Any AE for which there is evidence to suggest a causal relationship (reasonable possibility) between the drug and the AE. A suspected adverse reaction implies a lesser degree of certainty about causality than an adverse reaction.

*Adverse Reaction:* Any AE caused by the use of a drug. Adverse reactions are a subset of all suspected adverse reactions for which there is reason to conclude that the drug caused the event.

*Unexpected Adverse Reaction:* Any AE that is (a) not listed in the Investigator's Brochure, (b) not listed with the specificity and severity that is being observed, (c) not consistent with the risk information described in the general investigational plan or elsewhere in the current application (in the absence of an investigator brochure), and (d) listed as occurring with a class of drugs, but not specifically mentioned as occurring with the particular drug under investigation.

Adverse events may be treatment-emergent (i.e., occurring after initial receipt of investigational product) or nontreatment-emergent. A nontreatment-emergent AE is any new sign or symptom, disease, or other untoward medical event that begins after written informed consent has been obtained but before the subject has received investigational product.

### 10.2 Evaluation of Adverse Events

Adverse events include:

- Suspected adverse drug reactions
- Reactions from investigational product overdose, abuse, withdrawal, sensitivity, or toxicity
- Significant changes or abnormalities when compared to baseline, in signs, symptoms, clinical laboratory results, or physiological testing. This includes any worsening of a pre-existing condition temporally associated with the use of investigational product.
- Other untoward medical events, regardless of their relationship to the investigational product, such as injury, events that require surgery, accidents, extensions of symptoms, or apparently unrelated illnesses

The following items should be considered when identifying an AE:

- Anticipated day-to-day fluctuations of pre-existing conditions, including the disease under study, that do not represent a clinically significant exacerbation or worsening need not be considered AEs.
- In the event that a constellation of symptoms results in a confirmed diagnosis, the diagnosis (not the symptoms) should be recorded as the AE term.
- If a diagnosis cannot be established, the symptoms should be recorded as the AE(s).
- If an ongoing symptom has been included in the medical history, an associated severity grade and frequency should also be documented so that a worsening in severity or frequency of a symptom can be readily identified as an AE.
- Progression of disease is not itself an AE; however, the presenting sign or symptom of the disease progression should be documented as an AE (e.g. pleural effusion).  
*Exception:* If a subject experiences progression of disease that results in death, ‘progression of disease’ may be reported as an SAE if, by medical opinion, the term best describes the cause of death.

### 10.3 Determination of Seriousness

#### 10.3.1 *Serious Adverse Event (SAE)*

An AE is considered an SAE if any of the following conditions applies:

- Death: An AE that results in death during the active study period or within 30 days following investigational product administration. In addition, a reported death at any time post-study that is thought to be related to investigational product administration;
- Life-threatening adverse event: An AE that places the subject, in the view of the investigator, at immediate risk of death from the event as it occurred (i.e. this does not include a reaction that, had it occurred in a more severe form, might have caused death);
- Permanent, persistent, or significant disability: A disability is defined as any substantial disruption of a person’s ability to conduct normal life functions;
- Inpatient hospitalization or prolongation of existing hospitalization: In general, hospitalization refers to admission of a subject into a hospital for at least a 24-hour stay.

Hospitalizations for routine blood transfusions, hospitalization for an elective or diagnostic procedure, or surgery for a pre-existing condition that has not worsened, are not considered SAEs. (Emergency room visits that do not result with admission are not considered as SAEs);

- A congenital anomaly/birth defect in the offspring of a subject: A fixed, permanent impairment established at or before birth;
- An important medical event that may jeopardize the subject or may require medical intervention to prevent one of the outcomes listed above. Medical judgment should be used to decide if an adverse event should be considered an important medical event. Examples of medically important events are intensive treatment for allergic bronchospasm or convulsions that do not result in hospitalizations
- New cancer: Occurrence or diagnosis of a new cancer during the trial is considered an SAE. (This does not pertain to metastasis of current disease);
- Any AE associated with an overdose of the investigational product: An overdose of investigational product is defined as an occurrence of administered dose exceeding that which is prescribed by the investigator per protocol.

#### **10.3.2        *Non-Serious Adverse Event***

An AE that does not fulfill the criteria for a SAE is classified as a non-serious AE. See [Section 10.1](#).

#### **10.4        *Determination of Severity***

Assessment of severity is one of the responsibilities of the investigator in the evaluation of AEs and SAEs. The severity of AEs will be assessed according to the NCI CTCAE, v.4.03, which will be provided to the site as a separate document. If the AE is not defined in the NCI CTCAE, v.4.03, the investigator will determine the severity of an AE based on the following definitions:

- Mild (Grade 1): The AE is noticeable to the subject, but does not interfere with routine activity. The AE does not require discontinuing administration or reducing the dose of the investigational product.
- Moderate (Grade 2): The AE interferes with routine activity, but responds to symptomatic therapy or rest. The AE may require reducing the dose, but not discontinuing administration of the investigational product.
- Severe (Grade 3): The AE significantly limits the subject's ability to perform routine activities despite symptomatic therapy. In addition, the AE leads to discontinuing administration or reducing the dose of the investigational product.
- Life Threatening (Grade 4): The AE requires discontinuing administration of the investigational product. The subject is at immediate risk of death.
- Death (Grade 5): The subject dies as a direct result of the complication or condition

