For subjects with HER2- disease, the Ad-RTS-hIL-12 immunotherapy is intended to be given as a chemotherapy holiday, for example, to avoid intolerable or undesirable toxicity of the standard therapy. Ad-RTS-hIL-12 immunotherapy must be started within 4 weeks of stopping the pre-study standard chemotherapy.

Subjects with HER2+ disease will receive the Ad-RTS-hIL-12 immunotherapy in conjunction with first-, second-, or third-line anti-HER2 antibody therapy, i.e., subjects may continue anti-HER2-directed antibody therapy during the study period. Anti-HER2 antibody therapy will be administered according to the manufacturer's recommendations. Subjects with HER2+ breast cancer who continue the anti-HER2 antibody therapy need to recover from any anti-HER2 related AE/SAE, i.e., the event must have resolved to Grade 1 or baseline, before starting Ad-RTS-hIL-12 immunotherapy.

The Ad-RTS-hIL-12 immunotherapy cycle is a 21-day cycle comprised of investigational product administration on days 1 through 7 followed by rest on days 8 through 21. On day 1, enrolled subjects will receive the first dose of veledimex followed 3 hours  $\pm$  3 hours later by an intratumoral injection of Ad-RTS-hIL-12. The veledimex will continue to be given once daily on days 2 through 7 (see [Section 5](#) below, for details).

A safety review committee (SRC) will convene after every 5th subject with HER2- disease have completed the Ad-RTS-hIL-12 immunotherapy cycle (i.e., after each subject has completed 21 days on study). The SRC will also convene after the first 5 subjects with HER2+ disease have completed the Ad-RTS-hIL-12 immunotherapy cycle. The SRC will consist of the investigator, medical monitor, and other appropriate Sponsor representatives. The SRC will review all available safety information (AEs/SAEs, laboratory parameter data, ECG etc.). Tolerability will be evaluated separately for subjects with HER2- and HER2+ disease.

The safety evaluation will be based on the occurrence of related, treatment refractory Grade 3 and 4 AEs within 21 days following the start of Ad-RTS-hIL-12 immunotherapy. A post-treatment safety assessment visit will be conducted on Day 21.

The primary endpoint is safety/tolerability, defined as the proportion of patients who are able to complete 12 weeks on study without a Grade 3 or higher toxicity as defined by [Section 12.4.2](#).

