### 12.4.2 *Safety Analyses*

Exposure to investigational product and reasons for discontinuation of study treatment will be tabulated. All treatment-emergent AEs will be coded according to the system organ class and preferred term using the Medical Dictionary for Regulatory Affairs (MedDRA®), and will be tabulated by number and percent of subjects, and according to relationship to the investigational product, severity, and seriousness. ‘Treatment-emergent’ is defined as any AE that occurs during or after administration of the first dose of investigational product through the evaluation period for safety defined above, regardless of relationship to investigational product; or any event that is present at baseline that worsens in intensity or is subsequently considered to be drug related by the investigator.

Deaths, SAEs, and AEs resulting in patient discontinuation will be listed. Laboratory parameters, vital signs, and physical examination data will be summarized by visit. Data listings will be presented by visit.

Toxicity stopping rules ([Jennison and Turnbull, 2000](#); [Ivanova et al, 2005](#)), when applicable, will be determined based on a clinical assessment made by the SRC after a formal evaluation of safety data after every 5 subjects with HER2- disease have completed one cycle of Ad-RTS-hIL-12 immunotherapy. The SRC will review safety data separately for subjects with HER2+ disease to assess toxicity after the first 5 HER2+ subjects complete one cycle of Ad-RTS-hIL-12 immunotherapy.

The first stopping rule is based on related, treatment refractory Grade 3 or 4 adverse events. A rate of 50% is deemed unacceptable, a rate of 25% is deemed acceptable. The boundaries to stop the study are given as follows:

- If 4 of the first 5 patients have related, treatment refractory Grade 3 or 4 AE, stop the study.
- If 6 of the first 10 patients have related, treatment refractory Grade 3 or 4 AE, stop the study.
- If 8 of the first 15 patients have related, treatment refractory Grade 3 or 4 AE, stop the study.

- If 9 of the first 20 patients have related, treatment refractory Grade 3 or 4 AE, stop the study.
- If 11 of the first 25 patients have related, treatment refractory Grade 3 or 4 AE, stop the study.
- If 12 of the first 30 patients have related, treatment refractory Grade 3 or 4 AE, stop the study.
- If 14 of the first 35 patients have related, treatment refractory Grade 3 or 4 AE, stop the study.

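### For adverse events outside CTCAE v4.03, fallback Grade 3 requires that the product was stopped or reduced, so a severe event after Day 7 has no valid grade

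*Protocol*

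**What the plan says.** Protocol Section 10.4 makes CTCAE v4.03 the grading standard and adds a fallback: "If the AE is not defined in the NCI CTCAE, v.4.03, the investigator will determine the severity" from five definitions given there. Three of them matter here.

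- Fallback Grade 2: "The AE interferes with routine activity, but responds to symptomatic therapy or rest".
- Fallback Grade 3, first condition: "The AE significantly limits the subject's ability to perform routine activities despite symptomatic therapy". The second condition is introduced by the words 'In addition': "the AE leads to discontinuing administration or reducing the dose of the investigational product".
- Fallback Grade 4: "The AE requires discontinuing administration of the investigational product", together with immediate risk of death.

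Section 3.1 describes a 21-day cycle with "investigational product administration on days 1 through 7 followed by rest on days 8 through 21". The synopsis and Section 6.4 allow one cycle only, and Section 6.4 says that held or missed doses are not made up.

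The grade is used in two places. Section 12.4.2 states: "The first stopping rule is based on related, treatment refractory Grade 3 or 4 adverse events". Section 3.1 sets the window for that evaluation at 21 days from the start of immunotherapy. Section 3.1 also defines the primary endpoint as the proportion of patients who complete 12 weeks without Grade 3 or higher toxicity.

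**The concern.** A severity grade should describe how bad an event is. Fallback Grade 3 also asks what was done with the drug, and after the last dose nothing more can be done with it. Both windows that use the grade run well past that point.

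The gap falls on events that persist despite symptomatic therapy, and the stopping rule is meant to count treatment-refractory events. Any error goes in one direction. An event left ungraded lowers the count compared with the toxicity boundary and raises the proportion recorded as free of Grade 3 or higher toxicity.

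An analysis plan cannot easily repair this, because the investigator assigns the grade at the site from Section 10.4.

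**Working it through.** The protocol states no figure that depends on this definition, so there is none to reproduce. The check sets the grading text against the dosing period and the safety windows.

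**Step 1. Can fallback Grade 3 be met after Day 7?** Its two conditions are cumulative. The injection is given on Day 1 and veledimex on Days 1 to 7 (Sections 3.1 and 6.2). There is one cycle, and held doses are not made up (Section 6.4). From Day 8 there is no administration to discontinue and no dose to reduce, so the second condition fails however severe the event is.

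**Step 2. Does another grade fit?** Take an event with onset after Day 7 that significantly limits routine activity despite symptomatic therapy and is not immediately life-threatening.
- Grade 1 fails, because the event interferes with routine activity.
- Grade 2 fails, because the event does not respond to symptomatic therapy or rest.
- Grade 3 fails by Step 1.
- Grades 4 and 5 fail, because there is neither immediate risk of death nor death.

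No definition fits.

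**Step 3. How much of each window is exposed?** Counting from Day 1, with dosing over after Day 7:
- stopping-rule window, 21 days: (21 − 7)/21 = 14/21 = 67%;
- full adverse event collection to Week 6 (Section 10.9), 42 days: (42 − 7)/42 = 35/42 = 83%;
- primary endpoint window, 84 days: (84 − 7)/84 = 77/84 = 92%, although after Week 6 only serious events suspected to be related are collected.

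These are shares of calendar days.

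**Step 4. What would missed events do to the stopping rule?** The documents do not say what share of qualifying events would go ungraded, so this step is illustrative only. Take the boundaries in Section 12.4.2 (4/5, 6/10, 8/15, 9/20, 11/25, 12/30, 14/35, 15/40) as a single sequence of 40 patients with a look after every 5. If the true rate is 50% (the unacceptable rate) and a share m of events is missed, the counted rate is 0.50 × (1 − m). Exact binomial recursion over the eight looks gives:

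| Assumed share missed, m | Counted rate | Probability of crossing a boundary by n = 40 |
|---|---|---|
| 0 | 0.500 | 0.970 |
| 5% | 0.475 | 0.942 |
| 10% | 0.450 | 0.897 |
| 20% | 0.400 | 0.743 |

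With no events missed, the rule stops with probability 0.105 at the acceptable rate of 25%. The table shows how sensitive the rule is to under-counting. It does not show how much under-counting to expect. The 20% row in particular is hard to square with a problem confined to events outside CTCAE.

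**The case against.** The strongest reply is that the fallback may hardly ever be used. It applies only to events that CTCAE does not define. Sections 6.8 and 8.3.1.6 grade local reactions and record adverse events by CTCAE, and no event that would need the fallback can be named from the protocol. The early reactions described in Section 1.4.2, such as fever in the first 2 days and nausea on the day of injection, fall inside the dosing week. This stands. It limits the size of the problem, though it does not rule out delayed events.

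There are also safeguards. Serious events are reported whatever their grade. The safety review committee sees all available safety information, and Section 12.4.2 rests stopping on its clinical assessment. An ungraded severe event would therefore probably still be seen, and an investigator might grade it 3 by judgement. This stands in part: the written definition does not support that grade, and the stopping boundaries and the primary endpoint are counts of graded events.

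Three stronger readings are tempting, and the text does not support them.
- A reader might infer that late severe events drop to Grade 2. They cannot, because Grade 2 requires a response to symptomatic therapy or rest. The result is a gap, not a downgrade.
- A reader might infer that Grade 4 is lost in the same way. Its wording is similar, but it speaks of what the event requires, and immediate risk of death would probably settle the grade.
- A reader might take 67% or 83% as the share of toxicity that is missed. That would need onset spread evenly over the window and events that are all outside CTCAE. The documents support neither.

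**Conclusion.** The point holds as an error of definition with a limited practical effect. Read literally, fallback Grade 3 cannot be assigned from Day 8, and a severe, treatment-refractory event outside CTCAE then has no valid grade. Such an event would enter neither the 21-day stopping count nor the 12-week primary endpoint.

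The condition is out of reach on 14 of the 21 days of the stopping window. How many events this affects is not stated and is probably small. The conclusion rests on reading the two Grade 3 conditions as cumulative, which the wording requires, and on dosing ending at Day 7, which the protocol states. Events defined in CTCAE are unaffected. No stated figure in the protocol is contradicted. This is a minor correction, worth making because the error runs towards under-counting toxicity in the primary endpoint.

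**What to change.** Remove the drug-action clauses from every fallback definition in Section 10.4 that carries one, namely Grades 1, 2, 3 and 4, so that severity rests on clinical effect alone. Grade 1 must be included: if its clause stayed, an event that does not interfere with activity but led to stopping the product would have no grade.

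Record the action taken with the product separately, as Section 10.6 already requires. This reconciles Section 10.4 with the dosing period and the two safety windows, and changes no dosing or management rule.

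The cost is the deletion of a few clauses and needs no new data. The downside is that a few more events may be graded 3 and so count towards the boundary and the primary endpoint.
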